7.11.2.2 Mortality

Survival status will be collected up to Day 90 +/- 30 days. Death is considered as an event. All the mortality events and cause of death will be listed by treatment arm and by patient.

Patients who did not experience death within the first 90 days will be censored on the date of Day 90 visit or the date of last contact from the study which ever is earlier.

The number of patients who died and survival time will be summarized by treatment arm. Survival time will also be listed by patient. The probability function of death will be estimated by Kaplan-Meier method. The median time and its 95% confidence interval for each group will be reported. Cumulative progression rates estimated by the KM method for up to day 6, 14, 28, 90 and the 95% confidence intervals will be reported.

The hazard ratio will be estimated by the Cox proportional hazards model with treatment arm as a covariate in the model. Relevant hazard rates, hazard ratio between treatment arms and associated p-values will be tabulated.

7.11.2.3 Time to Improvement in Oxygenation

The secondary endpoint of time to improvement in oxygenation will be assessed in terms of the analysis in oxygenation parameters by visit. That is, evaluation of an improvement in oxygenation parameters will be assessed on the basis of the change from baseline analysis at the study timepoints of interest.

Oxygenation parameters including PaO_2/FiO_2 ratio, SpO_2/FiO_2 ratio and $P(A-a)O_2$ gradient (alveolar-arterial) will be measured at the Screening visit, any days the patient is hospitalized (and where data is available) from Day 1 through Day 28 and at Day 90. On days where arterial blood gas test data is not available, PaO_2 may be estimated using pulse oximetry when required for calculating the PaO_2/FiO_2 ratio.

Oxygen saturation (SpO₂), SpO₂/FiO₂ ratio, and PaO₂/FiO₂ ratio will be summarized, along with the change from baseline and percentage change from baseline, and at all available study visits during Days 1-6, Day 14, Day 28, and Day 90 (where available). See Sections 7.1.2, 7.1.3, and 7.1.4 for algorithm on determining assessments to be used for analysis.

Percentage change from baseline is defined as:

Percentage Change from Baseline= Change from Baseline/ Baseline

For the percent change from baseline in these parameters, deterioration is defined as a negative percent change from baseline, while improvement is a positive percent change from baseline.

Change in PaO₂/FiO₂ ratio will also be presented by waterfall plot.

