5.2.2 Secondary Endpoints

• Change in ordinal scale.

- All cause 28-day mortality.
- Number of patients with treatment-emergent serious adverse events or clinically significant adverse drug reactions (ADRs).
- Survival time and causes of death.
- Time to improvement in oxygenation (PaO₂/FiO₂ ratio, SpO₂/FiO₂ ratio and P(A-a)O₂ gradient).
- Rate of nosocomial infection (as determined by local institution practice).
- Duration of hospitalization.
- Number of patients requiring initiation of mechanical ventilation.
- Duration of invasive and non-invasive ventilation and/or supplemental oxygen.
- Time to normalization of WBC and lymphocytes.

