7.1 General Considerations

All safety analyses will be based on Safety Population; all efficacy analyses will be based on Modified Intent-to-Treat population, unless otherwise specified. Some specific sensitivity analyses of efficacy may be based on ITT and Per Protocol populations (for primary endpoints only). See Section 7.4 below for definitions of each analysis population.

All analyses will be considered as descriptive analyses. Derivation of two-sided 95% confidence intervals and p-values will be generated where applicable.

Time to event endpoints will be defined as the start date/time to the end date/time; censoring dates will be the last date/time the patient was determined to be event-free. Kaplan Meier methods will be used for time to event endpoint analyses; a log-rank test will be performed to compare the two survival curves. Timepoints estimates and median survival will be derived from the Kaplan Meier analysis. A Cox proportional hazards model may also be used to compare the two treatment arms using a hazard ratio.

Categorical endpoints will be calculated as the percentage of patients with the event, relative to the number of patients in a given analysis population (see Section 7.4). Stratified logistic regression approaches and/or repeated measures statistical approaches may be used to compare patients on the sargramostim and control arms, in addition to Fisher's Exact or Chi² tests (as appropriate). The randomization stratification factor for the baseline SOFA score (<6 versus \geq 6) will be considered for any stratified analysis.

Continuous endpoints will be summarized by n, means, medians, minimum, maximum, and 25th and 75th percentiles. Analysis of variance, analysis of covariance, and/or repeated measures statistical approaches may be used to compare patients on the sargramostim and control arms.

In the event that the underlying assumptions and/or distributions for a given statistical method are not satisfied, alternative statistical methods will be employed.

Additional exploratory analyses may be performed to evaluate the robustness and sensitivity of the study results, including but not limited to, additional evaluation of endpoints on other

analysis populations, subgroup analyses, treatment interactions, adjusted or stratified analyses, and/or alternative statistical methods.

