7.11 Efficacy Evaluations

The primary and secondary efficacy endpoints of the study (as defined above in Sections 5.2.1 and 5.2.2 above) will be analyzed as specified below. If the primary and secondary efficacy endpoints show meaningful results, then the exploratory efficacy endpoints (Section 5.2.3 above) will be summarized.

Key timepoints of interest for endpoints include Days 1-6, Day 14, and Day 28, where data are assessed and/or available, unless otherwise specified. All available efficacy data will be tabulated and presented for all patients in the Modified Intent-to-Treat (MITT) Population; see Section 7.4.

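### Two time-to secondary endpoints get no time-to-event analysis and no usable event definition in their own sections, and the nosocomial infection rate is left to a listing plus a general rule

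*SAP*

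**What the plan says.** SAP 5.2.2 has ten secondary endpoints. Three are times to an event: "Survival time and causes of death", time to improvement in oxygenation (for three parameters), and "Time to normalization of WBC and lymphocytes". A fourth relevant item is a rate: "Rate of nosocomial infection (as determined by local institution practice".

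Section 7.11 says that the primary and secondary endpoints "will be analyzed as specified below", and that the available efficacy data will be tabulated for the MITT population. Section 7.1 gives the general rules. For times to event, "Kaplan Meier methods will be used for time to event endpoint analyses", with a log-rank comparison; "Time to event endpoints will be defined as the start date/time to the end date/time", and "censoring dates will be the last date/time the patient was determined to be event-free". Categorical endpoints are reported as the percentage of patients with the event.

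The endpoint sections then state:
- 7.11.2.2 (mortality): Kaplan-Meier, median with 95% CI, estimates at fixed days and a Cox model.
- 7.11.2.3 (oxygenation): "The secondary endpoint of time to improvement in oxygenation will be assessed in terms of the analysis in oxygenation parameters by visit". Any positive percent change counts as improvement in the ratio parameters.
- 7.11.2.4 (nosocomial infections): a listing drawn from adverse events.
- 7.11.2.6 (WBC and lymphocytes): status relative to the normal range at available visits, as a summary table and listing.

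**The concern.** The endpoint list and the general methods promise one kind of analysis for two endpoints, and the sections that govern those endpoints specify another. A reader of the results who looks for how quickly oxygenation improved, or how soon blood counts normalized, would find mean changes and status counts by visit. These answer a different question and describe only patients still observed at each visit.

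If the analyst instead falls back on 7.1, the event must be defined at that point, in an open-label study where by-arm data may already be visible. The nosocomial rate has a milder form of the same problem: whether a by-arm percentage appears depends on someone invoking 7.1.

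**Working it through.** The plan gives no figure to reproduce for this point, and 7.2 says the sample size rests on no statistical assumptions. The check is a comparison of text.

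| Endpoint in 5.2.2 | General rule in 7.1 | Analysis in its own section |
|---|---|---|
| Survival time | Kaplan-Meier, log-rank | Kaplan-Meier, median, Cox (7.11.2.2) |
| Time to oxygenation improvement | Kaplan-Meier, log-rank | Change from baseline by visit (7.11.2.3) |
| Time to WBC/lymphocyte normalization | Kaplan-Meier, log-rank | Range status by visit, listing (7.11.2.6) |
| Nosocomial infection rate | Percentage with event | Listing (7.11.2.4) |

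**Count.** Time-to endpoints: 3; with a time-to-event analysis in their own section: 1; without: 3 − 1 = 2. Adding the nosocomial rate, 3 of the 10 secondary endpoints are affected.

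**Can 7.1 be applied as it stands?** It needs an event.
- Oxygenation: 7.11.2.3 gives only the sign of the change. The 33% cutoff in 7.11.1.1 belongs to the P(A-a)O₂ gradient up to Day 6, and that section allows others such as 25% or 50%.
- WBC and lymphocytes: 7.11.2.6 describes a three-level status at each visit, not a first in-range value. It does not say what happens to patients already in range at baseline.
- Nosocomial infection: the event is clear enough for a percentage. The adverse event tables in 7.12.1, by system organ class and preferred term, would not isolate these infections.

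**How would deaths be handled?** The 7.1 rule censors at the last event-free time. The default in 7.1.5 addresses only patients who are alive. Read together, they do not settle deaths before improvement or normalization. For hospital stay, 7.11.2.5 does raise the issue.

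**Illustration only: Kaplan-Meier with deaths censored.** Assume constant hazards over 28 days, a true proportion I that improves and a proportion D that dies first. The total cumulative hazard is −ln(1 − I − D), and the improvement share is I/(I + D). Then 1 − KM = 1 − exp[ln(1 − I − D) × I/(I + D)].

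For I = 60% and D = 20%: −ln(0.20) = 1.609; 1.609 × 0.75 = 1.207; 1 − exp(−1.207) = 70.1%, an excess of 10.1 points.

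| D | I = 50% | I = 60% | I = 70% | Excess (points) |
|---|---|---|---|---|
| 10% | 53.4% | 64.4% | 75.5% | 3.4 to 5.5 |
| 20% | 57.7% | 70.1% | 83.3% | 7.7 to 13.3 |

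The SAP gives none of these rates. The figures show why deaths need a stated rule; they do not measure an error in an analysis the SAP plans.

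**The case against.** The best defense is that the general rules fill the gaps and that 7.11.2.3 is open about what it does. Parts of this stand.

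- **Nosocomial rate.** A reader might infer that no rate will be reported. The document does not support that: 7.1 supplies a percentage and a test, 7.11 promises tabulation in the MITT population, and 7.11.2.4 does not say that the listing is the only output. What remains is that the endpoint's own section does not apply the rule.
- **Time origin.** A reader might infer that the clock has no start. One can be derived: 7.1.3 starts the efficacy period at first dose, and 7.1.1 sets first dose to randomization for controls. The origin differs between arms, but it is not open.
- **Deaths.** A reader might infer that the SAP directs deaths to be censored and so overstates improvement by the amounts illustrated. Sections 7.1 and 7.1.5 do not clearly say so, and the bias arises only if the analyst falls back on 7.1.
- **Normalization wording.** A reader might infer that 7.11.2.6 counts out-of-range values as normalized. It is more naturally a clumsy description of a three-level status.
- **Blood gas sampling.** Section 7.11.1 notes that arterial blood gas was required only at baseline and Day 6, which is a good reason to keep P(A-a)O₂ by visit. It does not extend to SpO₂/FiO₂, nor to WBC and lymphocyte counts, which 7.11.2.6 plans on hospital days.

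The defense fails on the two time-to endpoints. Section 7.11.2.3 expressly substitutes another analysis, and 7.11.2.6 does so in effect; neither supplies an event that 7.1 could use. The table shells are a separate document and may say more, so the point concerns the SAP text only.

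**Conclusion.** The concern holds as an inconsistency and a gap in specification. Two of three time-to endpoints have no time-to-event analysis in their own sections and no event to which the general rule could be applied, and one rate endpoint depends on a general rule that its section does not invoke.

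That count is the only magnitude the document itself supports. The bias figures are conditional on falling back on Kaplan-Meier, on censoring deaths, on constant hazards and on assumed rates. These are secondary endpoints and 7.1 and 7.2 call all analyses descriptive, so the consequence is modest. The SAP should still be changed, because a descriptive report should describe the quantities it names.

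**What to change.** 1. **7.11.2.4:** add n/N (%) of MITT patients with at least one nosocomial infection by arm, with risk difference and 95% CI; keep the listing. At 80 versus 40 patients the half-width is 1.96 × √[p(1 − p)(1/80 + 1/40)], or 8.3, 11.4 and 15.2 points for assumed rates of 5%, 10% and 20% in both arms. The table would therefore be imprecise, and should be read so.
2. **7.11.2.6:** add cumulative incidence by arm through Day 28 of the first in-range value, from randomization in both arms, separately for WBC and lymphocytes, among patients out of range at baseline, with death as a competing event. Keep the status table.
3. **7.11.2.3:** add the same analysis for SpO₂/FiO₂ improvement, with one numeric threshold written into the SAP before by-arm data are reviewed. The SAP offers no value for this ratio, so the sponsor must choose and justify one. Keep P(A-a)O₂ by visit. State whether PaO₂/FiO₂ also stays by visit, since it may rest on oximetry estimates. Make 5.2.2 match.
4. **Live discharge, for items 2 and 3:** do not treat it as uninformative censoring, because discharge is related to recovery. Handle it as a separate competing event. For item 3, counting live discharge without oxygen as improved is the alternative; use one as the main analysis and show the other as a sensitivity analysis.
5. **7.1:** name these analyses as exceptions to the Kaplan-Meier and log-rank rule.

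The cost is SAP wording and about four tables from data already collected, plus the sensitivity analysis. The downside is that event times are only as precise as routine-care sampling, and item 2 uses fewer patients.

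If no time-to-event analysis is intended, reword 5.2.2 and 7.1 so that the two time-to endpoints are by-visit summaries. That makes the plan consistent but adds no estimate; item 1 would still be needed.

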7.1.2 Baseline Definition

For both treatment arms, baseline is considered any observation that occurs prior to, or on the date of randomization, unless otherwise specified. That is, baseline date \leq randomization date.

Additionally, for the sargramostim arm, baseline assessments must also be prior to the first sargramostim dose date/time.

If there are multiple baseline assessments, the latest one will be used for analysis purposes.

For assessments on the day of first dose where time is not captured, a nominal pre-dose indicator, if available, will serve as sufficient evidence that the assessment occurred prior to first dose.

Assessments on the day of the first dose where neither time nor a nominal pre-dose indicator are captured, will be considered prior to the first dose if such procedures are required by the protocol to be conducted before the first dose.

In all summaries, change from baseline variables will be calculated as the post-treatment value minus the value at baseline. The % change from baseline will be calculated as (post-baseline value - baseline value) / baseline value x 100.

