7.11.1 Primary Efficacy Evaluations

For primary efficacy measures based on oxygenation parameters, the main timepoints of interest for analyses are baseline, up to Day 6 for P(A-a)O₂ gradient, and by Day 14 for rate of intubation, where data are available, unless otherwise specified.

See Sections 7.1.2, 7.1.3, and 7.1.4 for algorithm on determining assessments to be used for analysis.

As ABG was required only at baseline and at Day 6/Post-Treatment visit (or day of discharge if earlier), the number of patients with complete data at all study visit days is expected to quite limited. Therefore, the primary timepoint for analyses for data based on ABG will be up to Day 6.

7.11.1.1 Oxygenation Up to Day 6

The $P(A-a)O_2$ gradient will be derived using arterial blood gas assessment via arterial puncture at baseline and up to Day 6, or day of discharge whichever is earlier. See Sections 7.1.2, 7.1.3, and 7.1.4 for algorithm on determining assessments to be used for analysis.

The change from baseline and percentage from baseline is defined as:

Percentage Change from Baseline= Change from Baseline/ Baseline

The P(A-a)O₂ gradient, the percent change from baseline up to Day 6 will be tabulated based on "unchanged or deteriorated" [no difference or positive percent change from baseline] and "improved" [negative percent changer from baseline] by 10% change increments. In addition,

the percentage of patients with $a \ge 33\%$ improvement for each treatment arm will be provided. For both of these analyses, a Chi-square, or Fisher's exact test (or stratified logistic model) will be generated to compare the treatment arms. Alternative cutoffs for defining meaningful improvement may be used (e.g., 25%, 50%), with similar analyses methods as above.

The maximum change from baseline and maximum percentage change from baseline will be summarized up to Day 6, and for the study duration.

Maximum percentage change from baseline is defined as:

Maximum Percentage Change from Baseline= Maximum Change from Baseline/ Baseline

For these analyses, the baseline is defined as the last available assessment prior to administration of study drug (see Section 7.1.2 above). Except as noted in Section 7.1.1, unscheduled records will be excluded from the summaries at specific timepoints but will be included in the maximum change from baseline.

A listing of all P(A-a)O₂ gradient measurements will be provided.

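### In SAP 7.11.2.3, the improvement/deterioration rule covers SpO₂ with no account of FiO₂, and, separately, oximetry-estimated PaO₂ may be compared with an ABG-measured baseline

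*SAP*

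**What the plan says.** SAP 5.2.2 names the secondary endpoint as "Time to improvement in oxygenation (PaO₂/FiO₂ ratio, SpO₂/FiO₂ ratio and P(A-a)O₂ gradient". SpO₂ by itself is not in that list.

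SAP 7.11.2.3 says this endpoint will be assessed through change from baseline by visit. It then sets out the tables: "Oxygen saturation (SpO₂), SpO₂/FiO₂ ratio, and PaO₂/FiO₂ ratio will be summarized, along with the change from baseline and percentage change from baseline", on Days 1-6, 14, 28 and 90 where data exist. The direction rule follows and refers to the parameters just listed: "deterioration is defined as a negative percent change from baseline, while improvement is a positive percent change from baseline". It has no minimum size of change and no condition on FiO₂ or level of support. The same section plans a waterfall plot of change in PaO₂/FiO₂.

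For days without an arterial blood gas, 7.11.2.3 says that "PaO_2 may be estimated using pulse oximetry when required for calculating the PaO_2/FiO_2 ratio". SAP 7.11.1 explains how often that could arise: "As ABG was required only at baseline and at Day 6/Post-Treatment visit (or day of discharge if earlier"). SAP 7.1.2 fixes the baseline without separating measured from estimated PaO₂: "If there are multiple baseline assessments, the latest one will be used for analysis purposes". The SAP gives no conversion formula, no flag for estimated values and no ABG-only sensitivity analysis.

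**The concern.** There are two distinct problems.

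**Direction label on SpO₂.** Saturation reflects both lung function and the oxygen delivered. If support is raised, SpO₂ can rise while gas exchange worsens. If support is weaned, SpO₂ can fall a little while gas exchange recovers. A rule that looks only at the sign of the change in SpO₂ then gives the wrong label. The same set of tables can describe one patient at one visit as improved on SpO₂ and deteriorated on SpO₂/FiO₂, and nothing says which governs.

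**Unlike measurements in one change score.** Where the estimation option is used, change in PaO₂/FiO₂ on a day without ABG is an oximetry-derived value minus a measured one. The dissociation curve flattens at high saturation, so a small oximeter error becomes a large PaO₂ error there. Because the rule cuts at zero, that error alone can decide the label when little has truly changed. A waterfall plot that mixes the two kinds of value would not show it.

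At stake is the reading of the tables that the SAP itself makes the assessment of a secondary endpoint.

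**Working it through.** The SAP gives no figure on this point to reproduce. The check applies its own formula, change from baseline divided by baseline, to assumed patients.

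**1. SpO₂ against SpO₂/FiO₂ (all patient values assumed; room air taken as FiO₂ 0.21)**

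| Patient | SpO₂ change | Label by the rule | SpO₂/FiO₂ change |
|---|---|---|---|
| Escalated: 90% on 0.36 to 96% on 0.80 | 96/90 - 1 = +6.7% | improvement | 90/0.36 = 250 to 96/0.80 = 120; 120/250 - 1 = -52% |
| Escalated, smaller step: 90% on 0.40 to 93% on 0.50 | 93/90 - 1 = +3.3% | improvement | 225 to 186; -17.3% |
| Weaned: 97% on 0.60 to 94% on room air | 94/97 - 1 = -3.1% | deterioration | 97/0.60 = 162 to 94/0.21 = 448; +177% |
| Weaned, smaller step: 96% on 0.50 to 93% on 0.40 | 93/96 - 1 = -3.1% | deterioration | 192 to 232; +21.1% |

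The label reverses in all four, including the modest steps.

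**2. Does SpO₂/FiO₂ have the same problem?** SpO₂ cannot exceed 100. After FiO₂ goes from f0 to a higher f1, the ratio can rise only if baseline SpO₂ is below 100 × f0/f1:

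- 0.40 to 0.50: below 80.0
- 0.50 to 0.60: below 83.3
- 0.90 to 1.00: below 90.0

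In the other direction, for a patient at 96% weaned from 0.50 to 0.40, the ratio falls only if SpO₂ drops below 96 × 0.40/0.50 = 76.8. So the ratio largely avoids the reversal. It is least protected against small proportional steps at high FiO₂.

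**3. Error in estimated PaO₂ (assumed)**

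Assumptions: a standard dissociation equation, S = 100 / (23400/(p³ + 150p) + 1), with p the PaO₂ in mmHg, and an oximeter error of 2 points either way. Take the saturation at the true p, shift it by 2 points, and solve back for p. At p = 60, S = 100/(23400/225000 + 1) = 90.58. Solving at 92.58 gives p = 65.6, an error of 65.6/60 - 1 = +9%. Solving at 88.58 gives 55.7, an error of -7%.

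| True PaO₂ | Error in estimated PaO₂, 2 points low to 2 points high |
|---|---|
| 60 | -7% to +9% |
| 70 | -10% to +15% |
| 80 | -13% to +25% |
| 90 | -16% to +44% |

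With a 1-point error the ranges are about -4% to +4% at 60 and -7% to +10% at 80. FiO₂ is a common divisor, so the same relative error carries into PaO₂/FiO₂.

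**4. Effect on the sign.** Observed change = (1 + true change) × (1 + error) - 1.

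- True 0%, error +10%: observed +10.0%, labelled improvement.
- True -5%, error +10%: 0.95 × 1.10 - 1 = +4.5%, sign flipped.
- True -10%, error +20%: 0.90 × 1.20 - 1 = +8.0%, sign flipped.
- True -20%, error +20%: 0.80 × 1.20 - 1 = -4.0%, sign kept.

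The error can go either way and matters when the true change is small.

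**The case against.** The case for leaving the section alone is substantial.

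- The rule may be only a sign convention, needed because P(A-a)O₂ runs the other way in 7.11.1.1. Section 7.11.2.3 plans no count of improved patients and no test on the label. Where the SAP wants such a count it says so, as for P(A-a)O₂ in 7.11.1.1 and the ordinal scale in 7.11.2.1. **This stands.** A reader might infer that escalated patients will be counted as responders, but no such analysis is specified here. A sign convention that points the wrong way for one listed parameter still needs correcting.
- SpO₂ alone is not an endpoint parameter, and the two ratios under the same rule index FiO₂. **This stands** and confines the reversal to SpO₂.
- A reader might infer that estimated PaO₂ also makes escalated patients look improved and weaned patients look deteriorated. **The documents do not support that.** PaO₂/FiO₂ still divides by FiO₂, and the estimation error follows neither escalation nor weaning. It is a separate measurement-error problem.
- It is tempting to say that most values between the required ABG visits will be estimates, or that sicker patients will get more ABGs. **The SAP says neither.** Estimation is optional, and its frequency is not given. At Day 6, ABG is required, so that comparison should be measured against measured. The conversion method may also be in the protocol, which is not at hand.
- The largest errors arise at PaO₂ 80 to 90, while the trial enrols patients with acute hypoxemia. **Fair**, which is why the range at 60 and 70 is shown.
- "All analyses will be considered as descriptive analyses", and the primary P(A-a)O₂ is derived from ABG. **This limits the consequence**, although these tables remain the evidence for the endpoint.

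**Conclusion.** The concern holds as two separate, modest defects in a descriptive secondary analysis.

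**The rule is wrong as written for SpO₂.** It can label an escalated patient improved and a weaned patient deteriorated on that parameter: +6.7% against -52%, and -3.1% against +177%, in the illustrative patients. How many patients would be affected cannot be worked out from the SAP.

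**Using estimated PaO₂ against a measured baseline is a weakness that is cheap to remove.** Where the option is used, a 2-point oximeter error moves PaO₂/FiO₂ by about -7% to +9% at PaO₂ 60, -13% to +25% at 80 and -16% to +44% at 90. This rests on the assumed dissociation equation and the assumed oximeter error, neither of which comes from the SAP.

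Neither defect touches the primary P(A-a)O₂ or intubation analyses.

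**What to change.** In SAP 7.11.2.3:

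1. Remove SpO₂ from the improvement/deterioration rule and apply the rule to SpO₂/FiO₂ and PaO₂/FiO₂ only. Show SpO₂ beside the FiO₂ at the same assessment.
2. Base change in PaO₂/FiO₂, and its waterfall plot, on ABG-measured PaO₂ at both baseline and follow-up. Use SpO₂/FiO₂, already a named parameter of the endpoint, on days without ABG.
3. If estimated PaO₂/FiO₂ is still shown, state or cite the conversion formula, flag each estimated value, report these results separately, and subtract a baseline estimated from baseline SpO₂ by the same formula.

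The cost is SAP wording and table programming, with no new data collection. The downside is fewer PaO₂/FiO₂ values on days without ABG, where SpO₂/FiO₂ can carry the description.
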